7.3.1 Eligibility Criteria

7.3.1.1 Inclusion Criteria

Subjects will be enrolled if they meet all of the following criteria:

- 1. Male/Female subjects >2 and ≤6-year-old
- 2. Acute infectious rhinitis/rhinosinusitis for ≤48h before trial entry
- 3. Patient presenting with fever ≥ 37.5 °C at screening
- 4. Subjects with nasal congestion (blocked / stuffy nose) rated at least as moderate on the Acute Rhinitis Symptoms Severity Questionnaire, based on evaluation by the investigator
- 5. Subjects showing at least moderate grade for at least one of the following additional signs of acute rhinitis: runny nose, nasal crust (dry mucus), sneezing and cough
- 6. Written consent obtained from parent/legal guardians

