The investigator will provide the parents/legal guardians with the device according to the site specific treatment list, in order to respect the 1:1 randomization (blocks of 4). The investigator will explain how to use it.

NB: The first use of the device will be performed in the evening of the Day 1.

D1-D8 up to -D11 (at home):

The Parent/legal guardian will be asked to complete the ARSSQ in the diary, once daily in the evening. The symptoms occurring from the morning to the evening should be taken into consideration. The ARSSQ shall be scored at least from D1 to D8. Adverse events/incidents and concomitant medications are to be reported during the whole period

Between D8 and D11 (at home):

End of Healsea® Babykids/Placebo nasal spray.

➤ NB: The last study nasal spray intake will be performed **between D8 and D11** in the morning. The patient should stop taking the investigational device before D11 only if the question 1 "not sick" of the ARSSQ is ticked YES for 2 consecutive days.

Up to D15/D18 (at home):

Parents/legal guardians will continue to complete the paper diary daily (incidents/adverse events/expected undesirable sides effects, concomitant medications). For patients for whom common cold symptoms persist, parents/ legal guardians will be instructed to continue to complete the ARSSQ, until the subject feels not sick for two consecutive days.

Visit 2 (V2) - (Day 15-Day 18): end of study

The investigator or his/her delegated designee will:

- Perform a physical and clinical examination.
- Collect the patient diary.
- Review the paper diary to validate adverse events pertinent in the context of the common cold, incidents linked to medical device use and concomitant medications reported by the parents/legal guardians. Complete the e-CRF accordingly and report any new relevant safety events
- Ask parents/legal guardians to complete the ARSSQ if the patient still has symptoms.
- Assess the compliance to the treatment by weighing the device bottle returned by the parents/legal guardians. If a nasal spray is not returned or lost, the investigator will ask the

Version 1.1 –2023.02.02 Page **37** of **64**

Study Number: LPH-2202

parents/legal guardians to specify the number of missed nasal spray uses and will report the data into the e-CRF.

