6.4. General conventions and/or calculated variables

6.4.1. Patient reference start/end dates

For each patient, the reference dates will be the following:

- The reference start date is the date of inclusion visit.
- The reference end date is the date when patient was determined to have ended the trial.

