6.4.4. Missing start/end dates of adverse events / incidents

In the following paragraphs, adverse events and incidents will be referred to as "adverse events" for ease of reading.

a) Start date

Completely missing date: it will be estimated by the reference start date.

If the day and the month are missing:

- If the year = year of reference start date, it will be estimated by the reference start date
- If the year < year of reference start date, it will be estimated by the 31st December
- If the year > year of reference start date, it will be estimated by the 1st January

If only the day is missing:

- If the month/year = month/year of reference start date, it will be estimated by the date of reference start date
- If the month/year < month/year of reference start date, it will be estimated by the last day of the month
- If the month/year > month/year of reference start date, it will be estimated by the first day of the month

If after imputation, the estimated start date is after the end date of the adverse event, it will be replaced by the end date of the adverse event.

b) End date

Note: the following rules concern events that are not "ongoing" at the end of the study.

Completely missing date: it will be estimated by the reference end date

If the day and the month are missing:

- If the year = year of reference end date, it will be estimated by the reference end date
- If the year < year of reference end date, it will be estimated by the 31st December
- If the year > year of reference end date, it will be estimated by the 1st January

If only the day is missing:

- If the month/year = month/year of reference end date, it will be estimated by the reference end date
- If the month/year < month/year of reference end date, it will be estimated by the last day of the month
- If the month/year > month/year of reference end date, it will be estimated by the first day of the month

If after imputation, the estimated end date is before the start date of the adverse event, it will be replaced by the start date of the adverse event.

AXIODIS CRO 12/47

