Since the computed duration in the three cases is a recovery time and not a survival time, unlike the usual case of application of Cox survival regression, the provided hazard ratios will measure the likeliness of the recovery.

Consequently, and particularly for the treatment (with Placebo as reference), a hazard ratio greater than 1 will have to be considered under a positive aspect, because it will significate that the recovery is more likely under Healsea[®] Babykids treatment than under Placebo. On the contrary, a hazard ratio lower than 1 will have to be considered under a negative aspect.

For the three durations, a forest plot of the hazard ratios and their 95% CIs from the final multivariate Cox survival regression model will be provided.

AXIODIS CRO 19/47

In addition, for the three durations, a Kaplan-Meier graph will be provided. Survival curves will be drawn by treatment group. Number of sick / symptomatic / impacted patients, number of events (recoveries) and number of censors in each arm will be displayed on the same graph, as well as the log-rank p-value.

For the same reason as above and unlike the usual case of application of Kaplan-Meier graph, if the log-rank p-value is under 5%, a survival curve for Healsea[®] Babykids group under the curve for Placebo group will have to be considered under a positive aspect, and the contrary under a negative aspect.

Patients will be analysed on the FAS.

AXIODIS CRO 20/47

Statistical Analysis Plan

10.2.3. Use and number of days of use of conventional common cold medications

A multivariate logistic regression model will be used to analyse use (yes/no) of conventional common cold medications (overall and by therapeutic class: antibiotics, antipyretics, mucolytics, decongestants, antitussives, systemic and topical corticosteroids).

BASICC

A multivariate Poisson regression model will be used to analyse the number of days of use of conventional common cold medications (overall and by therapeutic class).

The number of days of use of these medications is defined as follows:

- A day is counted when the patient used at least one of these medications this day;
- Each day is counted once, whatever the number of these medications used this day;
- The total number is the sum of all distinct days of use of these medications, from D1 to D18.

Patients will be analysed on the FAS.

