10.3. Concomitant treatments

Concomitant treatments are coded using the WHO-DRUG dictionary version 2022 Q1.

All treatments taken at least once from reference start date or appeared during the study will be summarised by Anatomical Therapeutic Class (ATC) and substance name. The number and percentage of patients in each category will be computed.

Patients will be counted only once within these ATC categories. They will be analysed on the FAS, by treatment group and overall.

Note: A medication which began strictly before reference start date and is on-going after reference start date is counted only in "previous medications" (see §8.2) and not in "concomitant medications".

AXIODIS CRO 21/47

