XXXXXXX	XX (XX.X%)	XX (XX.X%)	XX (XX.X%)

Mock L2

ID – Sex – Age	Treatment	Safety Set	Full Analysis Set	Per Protocol Set	Reason of withdrawal

AXIODIS CRO 34/47 Study Number: LPH-2202

BASICC

Mock T4

	Healsea Babykids N=XX	Placebo N=XX	Total N=XX
Age (years)			
N	XX	XX	XX
Missing	XX	XX	XX
Mean (SD)	XX.X (XX.X)	XX.X (XX.X)	XX.X (XX.X)
Median	XX	XX	XX
Q1/Q3	XX / XX	XX / XX	XX / XX
Min/Max	XX / XX	XX / XX	XX / XX
Sex			
N	XX	XX	XX
Missing	XX	XX	XX
Female	XX (XX.X%)	XX (XX.X%)	XX (XX.X%)
Male	XX (XX.X%)	XX (XX.X%)	XX (XX.X%)

Mock T5

ATC1 - ATC2	Healsea Babykids N=XX	Placebo N=XX	Total N=XX
Patients with at least one previous / concomitant	medication		
All	XX (XX.X%)	XX (XX.X%)	XX (XX.X%)
XXXXX			
All	XX (XX.X%)	XX (XX.X%)	XX (XX.X%)
XXXXX	XX (XX.X%)	XX (XX.X%)	XX (XX.X%)
XXXXX	XX (XX.X%)	XX (XX.X%)	XX (XX.X%)

Mock T6

	Healsea Babyki N=XX	ls Placebo N=XX	Total N=XX
Is the patient currently taking antibiotics or has the patie	nt taken antibiotics within 2 weeks before screenin	g?	•
N	XX	XX	XX
Missing	XX	XX	XX
No	XX (XX.X%) XX (XX.X%)	XX (XX.X%)
Yes	XX (XX.X%) XX (XX.X%)	XX (XX.X%)
Is the patient currently taking systemic corticosteroids or	has the patient taken systemic corticosteroids wit	hin 4 weeks before scree	ening?
N	XX	XX	XX
Missing	XX	XX	XX
No	XX (XX.X%) XX (XX.X%)	XX (XX.X%)
Yes	XX (XX.X%) XX (XX.X%)	XX (XX.X%)
Has the patient a chronic use of decongestant?			
N	XX	XX	XX
Missing	XX	XX	XX
No	XX (XX.X%) XX (XX.X%)	XX (XX.X%)
Yes	XX (XX.X%) XX (XX.X%)	XX (XX.X%)
Has the patient taken any medicine (in the previous 48 ho	ours) that could modify the ARSSQ assessment?		
N	XX	XX	XX
Missing	XX	XX	XX
No	XX (XX.X%) XX (XX.X%)	XX (XX.X%)
Yes	XX (XX.X%) XX (XX.X%)	XX (XX.X%)

AXIODIS CRO 35/47

Statistical Analysis Plan Final version – August 09th, 2023

Mock T7

	Healsea Babykids N=XX	Placebo N=XX	Total N=XX
Has the patient taken / has the patient been prescribed any treatment for first symptoms of	f infectious rhinitis?		
N	XX	XX	XX
Missing	XX	XX	XX
No	XX (XX.X%)	XX (XX.X%)	XX (XX.X%)
Yes	XX (XX.X%)	XX (XX.X%)	XX (XX.X%)

Mock T8

SOC - Preferred Term	Healsea Babykids N=XX	Placebo N=XX	Total N=XX			
Patients with at least one medical history						
All	XX (XX.X%)	XX (XX.X%)	XX (XX.X%)			
XXXXX						
All	XX (XX.X%)	XX (XX.X%)	XX (XX.X%)			
XXXXX	XX (XX.X%)	XX (XX.X%)	XX (XX.X%)			
XXXXX	XX (XX.X%)	XX (XX.X%)	XX (XX.X%)			

AXIODIS CRO 36/47

Mock T9

	Healsea Babykids N=XX	Placebo N=XX	Total N=XX
How sick does your child	I feel today?		
N	XX	XX	XX

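### SAP 10.2.3 counts cold-medication days from D1, although the first spray is that evening, and gives the yes/no model no window; this can dilute a descriptive secondary comparison by an unknown amount

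*SAP*

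**What the plan says.** A secondary objective is the device's effect on intake of conventional cold medication. SAP 10.2.3 gives it two models, each run overall and by therapeutic class: logistic for use (yes/no) and Poisson for days of use.

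- **Day count (SAP 10.2.3).** "A day is counted when the patient used at least one of these medications this day". The window follows: "The total number is the sum of all distinct days of use of these medications, from D1 to D18". Nothing separates hours before the spray from hours after it.
- **Yes/no use (SAP 10.2.3).** No window is stated.
- **First exposure (protocol 7.4.1).** "The first use of the device will be performed in the evening of the Day 1".
- **Anchor (SAP 6.4.1).** The reference start date "is the date of inclusion visit", that is, D1 and not the first spray.
- **Ongoing drugs (SAP 10.3).** "A medication which began strictly before reference start date and is on-going after reference start date is counted only in" the previous-medication table. SAP 10.2.3 does not refer to this note, and the note does not cover a drug begun on D1.
- **Missing start dates (SAP 6.4.5, applying 6.4.4).** "Completely missing date: it will be estimated by the reference start date", which puts such a medication on D1.
- **Covariates (SAP 10.2).** The candidates are baseline temperature and baseline scores of ARSSQ items 2 to 7. No medication term is included.
- **Baseline treatment (SAP 8.2, Mock T7).** One item, "Has the patient taken / has the patient been prescribed any treatment for first symptoms" of rhinitis, is summarised only.

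**The concern.** Protocol 7.1.4 expects less medication because symptoms should be shorter. Use before the first spray cannot carry that effect, yet most of D1 is unexposed time inside the counting window. If the yes/no model takes the same window, one dose on D1 makes a child a user of that class whatever happens later. A child whom the device would have spared later doses is then indistinguishable from one it did not help.

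D1 use is plausible. Protocol 7.3.1.1 lists "Patient presenting with fever ≥ 37.5 °C at screening" as an inclusion criterion, and protocol 7.4.2.1 permits all the analysed classes (decongestants as local ones). What is at stake is interpretation: a null medication result could partly reflect the counting window rather than the device.

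**Working it through.** **The plan's own figure.** The documents give no rate, effect size or power for medication use. The only sample-size statement (protocol 6.4, SAP 4) concerns the AUC: 100 per arm, standardised difference 0.4, 80% power, 5% error. It reproduces: n = 2(1.960 + 0.842)²/0.4² = 98.1, so 99 per arm (99.1 by the t-test), with power at 100 per arm of 80.7% (z) or 80.4% (t). This point does not affect it.

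**Yes/no use.** Let p0 and p1 be the shares using a class after the first spray (placebo, active), and q the share using it on D1 before the spray, equal in expectation by randomisation. Any use from D1 is later use plus D1-only use, so

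observed difference = (p0 − p1) − (D1-only share, active − D1-only share, placebo).

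If the device does nothing, the D1-only shares are equal and the difference stays zero, so type I error is not inflated. If the device reduces later use among D1 users, the D1-only share is larger on active and the gap shrinks.

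If D1 use is independent of later use, the D1-only share is q(1 − p), any use is q + (1 − q)p, and the gap becomes (1 − q)(p0 − p1). With assumed p0 = 60%, p1 = 40% and 100 per arm (two-sided 5%, power shown only as a yardstick):

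| q (assumed) | Placebo | Active | Gap (points) | Odds ratio | Power |
|---|---|---|---|---|---|
| 0 | 60% | 40% | 20 | 0.44 | 81% |
| 0.2 | 68% | 52% | 16 | 0.51 | 64% |
| 0.4 | 76% | 64% | 12 | 0.56 | 46% |
| 0.6 | 84% | 76% | 8 | 0.60 | 29% |

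Example, q = 0.4: 0.4 + 0.6 × 0.60 = 0.76; 0.4 + 0.6 × 0.40 = 0.64; odds ratio (0.64/0.36)/(0.76/0.24) = 0.56. With 50/30% or 70/50% instead, power at q = 0.4 is 42% or 51%, against 83% at q = 0.

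**Dependence on overlap.** Independence is an assumption. If every D1 user is also a later user, any use stays at 60% vs 40% and nothing is lost. That is possible only while q is at most 40%, the later-use share on active. At q = 0.6 with the greatest possible overlap, any use is 60% in both arms and the gap disappears. The loss can therefore be smaller or larger than in the table.

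**Days of use.** With mean days m0 and m1 after the spray and k counted days stemming from D1 use, rate ratio = (m1 + qk)/(m0 + qk). Assumed means are 4 vs 3 days (0.75 without D1 use):

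| k | q = 0.2 | q = 0.4 | q = 0.6 |
|---|---|---|---|
| 1 (D1 only) | 0.76 | 0.77 | 0.78 |
| 5 (course fixed at V1) | 0.80 | 0.83 | 0.86 |

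Example, q = 0.4: 3.4/4.4 = 0.77 for k = 1; 5/6 = 0.83 for k = 5. The difference in mean days stays at 1.0 throughout.

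**The case against.** The case for leaving the plan alone is substantial.

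- **Prescription is not use.** A reader might infer that any drug prescribed at V1 makes a child a user before the device can act. The documents do not support this: SAP 10.2.3 counts only days on which a drug was used. A prescription first filled on D2 is not use before the spray. Nor does Mock T7 show that prescribing at V1 is common.
- **The explicit window governs only the day count**, where D1 adds at most one day per child. The larger effect is in the yes/no model, where D1–D18 has to be inferred. This stands; the missing window is itself part of the point.
- **Entry criteria limit earlier use.** Protocol 7.3.1.2 excludes recent antibiotics, recent systemic corticosteroids and chronic decongestant use. It also excludes cold medicines in the previous 2 days if the investigator thinks they may influence the ARSSQ. The last is discretionary, and none limits doses between V1 and the evening. The fever argument is weaker than it looks: the synopsis omits that criterion, and SAP 8.5 tabulates fever as present or absent.
- **SAP 10.3 may seem to contradict 10.2.3.** It does not. It is a descriptive table with another purpose. What is missing is a statement on whether its note applies to the models.
- **D1 is a conventional anchor**, used elsewhere in the SAP for the AUC and the duration of the common cold. That is fair, but does not make use before the spray informative about the device.
- **Consequence.** SAP 6.3.1 makes secondary results descriptive, with p-values for information. This stands and limits the weight of the point.

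**Conclusion.** The point holds in a limited form. Doses taken on D1 before the first spray enter the day count and, if the same window is meant, the yes/no outcome. No covariate or exclusion removes them. They cannot reflect a device effect and can only dilute a difference, mainly in the yes/no odds ratio and only to the extent that D1 users are not also later users. For days of use, D1 alone has little effect.

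The size cannot be derived from the documents: every use rate, mean and course length above is an assumption, as is independence between D1 and later use. A reader might infer that the logistic analyses would mostly describe prescribing at the visit. That would need high D1 use, for which the documents give no evidence. Type I error and the primary conclusion are untouched. This is an inexpensive clarification of a secondary, descriptive analysis.

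**What to change.** In SAP 10.2.3, preferably before the blind is broken:

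1. State one window, D2 to D18, for both models: any use of the class on D2–D18, and number of days of use on D2–D18.
2. Tabulate use on or before D1 by arm and class, and offer it as a baseline covariate. Take it from the dated medication records (listing 16.2.6.2.1.1), since Mock T7 is a single yes/no item without class. Flag start dates imputed to D1.
3. Say whether the SAP 10.3 note on ongoing medications applies to 10.2.3.
4. Keep D1–D18 as a sensitivity analysis.

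Yes/no use should not be defined as a class newly started on D2 or later. A child with one D1 dose and many later days would then never count as a user of that class, while a drug prescribed at V1 and first taken on D2 would.

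The cost is SAP wording, a date filter and one extra table on data already collected. Two limits remain: D1-evening use after the spray is left out of the main analysis, and courses prescribed at V1 still contribute days from D2.

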3. STUDY DESIGN

This is a prospective, interventional, double-blinded, placebo controlled, randomized, national (Bulgaria), multicentre PMCF study.

The study comprises two parts:

- Part 1 (D1-D11): treatment of the acute phase, with **Healsea**® **Babykids** or with **isotonic nasal spray** (**Placebo**), 2 puffs in each nostril 2 times per day with a minimum of 7-day-treatment period (14 intakes of the investigational device) up to 10 days (20 intakes of the investigational device);
- Part 2 (up to D15/D18): follow-up phase.

Investigational plan description (see Figure 1):

- Visit 1 (V1) – (Day 1): Screening/Inclusion/Randomization

Information and provision of the information sheet to legal guardians/parents of participants, consent signature, demographic data and medical history, ongoing medication, inclusion/non-inclusion criteria, physical and clinical examination, baseline assessment of the ARSSQ, randomization, diary presentation, treatment dispensation of **Healsea**® **Babykids** Nasal Spray or **Placebo (Isotonic nasal spray)** (according to randomization list).

AXIODIS CRO 7/47

D1-D8 up to D1-D11 (at home):

Daily completion of the paper diary (questionnaire, adverse events/incidents and concomitant medications), Healsea® Babykids / Placebo nasal spray treatment daily administration.

Between D8 and D11 (at home):

End of Healsea® Babykids / Placebo nasal spray treatment.

Up to D15/D18 (at home):

Daily completion of the diary (adverse events/incidents, concomitant medications, ARSSQ if applicable, until the patient feels not sick for two consecutive days).

Visit 2(V2) - (Day 15-18): end of study

Diary review, reporting of the adverse events/incidents, compliance, ARSSQ completion if "not sick" is not ticked for two consecutive days in the previous days.

The maximal study duration for each patient is 18 days.

	Acute p	Acute phase Follow-up phas		phase
Visit name	Screening/Inclusion	At home	At home	End of study
Visit Number	V1		***************************************	V2
Days	D1	D1 to D11	D12 to End of study	D15-D18
Informed consent	х			
Eligibility criteria	х			
Demography and Medical history ***	x			
Physical and clinical examination	х			x
Baseline assessment of the Acute Rhinitis Symptoms Severity Questionnaire	х			
Ongoing medication	x			
Randomization	х			
Treatment (Healsea® Babykids or Placebo)	Х*	Χ#		
Subject paper diary (Acute Rhinitis Symptoms Severity Questionnaire**)				

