6.3.5. Handling of dropouts and missing data

a) Repositioning of visits

Not applicable.

b) Partially filled scales and missing data (other than ARSSQ and dates)

Concerning dates and ARSSQ, see §6.4.

No imputation will be done. Missing data will not be estimated and will be treated as missing data for the statistical analysis.

c) Dropouts

Patients from FAS who prematurely discontinued the study will be included in the analysis.

Except for ARSSQ and dates, no method will be applied to replace missing data.

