10.2. Analysis of the secondary efficacy criteria

The analysis of the secondary efficacy criteria will involve multivariate analysis.

The selection of variables in multivariate analysis will be performed using a 0.20 significance level and a stepwise method. Covariates considered as potential confounding factors to be initially tested with the treatment in the multivariate models are:

- Body temperature at baseline (°C);
- Scores to each of the items 2 to 7 of the ARSSO at baseline.

All multivariate analyses below will follow this logic.

10.2.1. Modelling of AUC on global score by multivariate ANCOVA

A multivariate ANCOVA model of the AUC on global score of ARSSQ during the first eleven days of the study will be performed.

Patients will be analysed on the FAS and the PP Set.

AXIODIS CRO 17/47

10.2.2. Durations of cold symptoms and of impacts on Quality-of-Life

Hereinafter, the "recovery date" is the first day of the two first consecutive days the patient gave a negative answer to the question 1 ("not sick") without giving a positive answer to the same question (other than "not sick") later. Otherwise, there is no "recovery date" for the patient.

The scores of cold symptoms and of impact on Quality-of-Life (QoL) will be computed at each time-point the patient completed the questionnaire (see §6.4.6), using the following formulae:

At each time point t: ARSSQ_{SYMP}(t) =
$$\sum_{j \text{ in } \{2; ...; 7\}} ARSSQ_{j}(t)$$

ARSSQ_{QOL}(t) = $\sum_{j \text{ in } \{8; ...; 10\}} ARSSQ_{j}(t)$

• The duration of common cold is defined as the duration between the reference start date and the recovery date.

Common cold's duration (days) = Recovery date - Reference start date

The origin date will be the reference start date.

The considered event is the end of common cold, i.e. the recovery of the patient. The event date will be the last day before the recovery date.

Patients without recovery date will be censored at D18 or at the end of the study, and the censoring date will be the date of D18 or the reference end date, whichever occurs first.

• The duration of the cold symptoms is defined as the duration between first symptomatic day and last symptomatic day.

Cold symptom's duration (days) = Last symptomatic day - first symptomatic day + 1

The first symptomatic day is the first day the patient had a non-zero and non-missing score of cold symptoms. It will be the origin date.

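### Days of cold-medication use are summed over D1–D18 in a Poisson model with no exposure term, although observation ends at V2 (D15–D18) or at withdrawal

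*SAP*

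**What the plan says.** SAP 10.2.3 analyses the number of days of use, overall and by therapeutic class, by multivariate Poisson regression on the FAS. The rule for adding a day is "A day is counted when the patient used at least one of these medications this day", and the window is fixed: "The total number is the sum of all distinct days of use of these medications, from D1 to D18". No offset or exposure term is given. The candidate covariates in SAP 10.2, introduced by "Covariates considered as potential confounding factors to be initially tested with the treatment in the multivariate models are", are baseline temperature and baseline ARSSQ items 2 to 7, so observed time is not among them.

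Follow-up is not fixed at 18 days. SAP 3 gives "Visit 2(V2) - (Day 15-18): end of study" and describes 18 days as a maximum. Protocol 7.4.1 has the same visit window, "Visit 2 (V2) - (Day 15-Day 18): end of study", and one task at that visit is "Collect the patient diary"; that diary is the source for medication use (Protocol 7.1.4 and 9.1). Under Protocol 7.3.1.3, children withdrawn by the investigator have a premature end-of-study visit and their available data are kept. SAP 6.3.5 adds: "Patients from FAS who prematurely discontinued the study will be included in the analysis". The same section says that missing data other than ARSSQ and dates are not replaced, but gives no rule for days after a child's end of study.

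The duration endpoints in SAP 10.2.2 are handled differently: children without the event are censored at the earlier of D18 and the reference end date.

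**The concern.** The counting rule has two outcomes for a day: recorded use adds 1, anything else adds 0. It has no third state for a day on which nobody was recording. A child whose V2 falls on D15 has 3 unobserved days in the window, and a child who leaves on D4 has 14. As written, these add the same as observed days without medication, so shorter observation looks like less rescue use.

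The effect on medication intake is a named secondary objective, and Protocol 7.1.4 expects the device to reduce rescue use. If one arm loses more children early, that arm gains an artificial advantage on this endpoint. The yes/no logistic model shares the gap for early leavers.

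**Working it through.** **The plan's own figure.** The only design calculation is for the primary AUC endpoint: 100 per arm, d = 0.4, two-sided 5%, power 80%. Check: 0.4 × √(100/2) = 2.828; 2.828 − 1.960 = 0.868; Φ(0.868) = 80.7% (80.4% with the t distribution). It reproduces and is unaffected by this point. No calculation is given for medication days.

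**Unobserved share of the 18-day window**, (18 − last observed day)/18:
- V2 on D15: 3/18 = 16.7%; D16: 2/18 = 11.1%; D17: 1/18 = 5.6%; D18: 0.
- Withdrawal on D4: 14/18 = 77.8%; D6: 12/18 = 66.7%; D8: 10/18 = 55.6%.
- V2 spread evenly over D15–D18 (assumed): mean observed time (15 + 16 + 17 + 18)/4 = 16.5 days, so 8.3% is unobserved with no withdrawals.

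**Spurious ratio with no true effect, front-loaded use.** Assumptions, none from the documents: daily use 30% on D1–D8 and 5% after; V2 even over D15–D18; withdrawal day uniform on D2–D8 (mean 5); 10% withdrawal in one arm and 2% in the other. Without an offset, the expected treatment ratio is the ratio of mean counts. With a log(observed days) offset, it is the ratio of total use to total observed days.
- Completer: 8 × 0.30 + 8.5 × 0.05 = 2.825 days of use in 16.5 observed.
- Leaver: 5 × 0.30 = 1.5 in 5 observed days if the withdrawal day is recorded, or 4 × 0.30 = 1.2 in 4 if not.

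| | Withdrawal day recorded | Not recorded |
|---|---|---|
| Mean use, 10% arm | 0.9 × 2.825 + 0.1 × 1.5 = 2.6925 | 2.6625 |
| Mean use, 2% arm | 0.98 × 2.825 + 0.02 × 1.5 = 2.7985 | 2.7925 |
| Ratio, no offset | 0.962 | 0.953 |
| Observed days, 10% arm | 0.9 × 16.5 + 0.1 × 5 = 15.35 | 15.25 |
| Observed days, 2% arm | 0.98 × 16.5 + 0.02 × 5 = 16.27 | 16.25 |
| Ratio, with offset | 0.1754/0.1720 = 1.020 | 0.1746/0.1718 = 1.016 |

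With the arms swapped, the ratios are 1.039–1.049 without the offset and 0.981–0.984 with it. Equal withdrawal gives 1.00. On the log scale the bias falls from 0.039 to 0.020, or from 0.048 to 0.016: by about half to two thirds, with a change of sign.

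**Other assumptions.**
- Constant daily rate, withdrawal on D6: 5% v 10% gives 15.45/15.975 = 0.967, and 5% v 15% gives 14.925/15.975 = 0.934. Here the offset restores 1.00.
- Use decaying with a half-life of 3 to 5 days: 95% to 98% of use falls by D15, and withdrawal of 5% v 15% on D4 or D6 gives 0.95–0.98.

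**V2 timing alone, worst case.** One arm seen entirely at D15 and the other entirely at D18 gives 2.75/2.90 = 0.95 under the front-loaded rates and 15/18 = 0.83 under a constant rate. Nothing in the design would produce such a split.

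**Against sampling noise.** With independent days, a completer's variance is 8 × 0.30 × 0.70 + 8.5 × 0.05 × 0.95 = 2.08. The SE of the log ratio at 100 per arm is then about √(2 × 2.08/(100 × 2.825²)) = 0.072. The bias of 0.039–0.048 is roughly half to two thirds of one SE.

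**The case against.** No sentence in the SAP says that unobserved days are drug-free. D1–D18 can be read as the outer limit of the window, since 18 days is a maximum, and SAP 6.3.5 says missing data stay missing. This stands as far as wording goes: a reader might infer an explicit zero-fill rule, and the documents do not contain one. But the alternative, that an incompletely observed count is missing, would drop every child seen before D18 and conflicts with keeping discontinued FAS patients in the analysis. Mock T16 has a row for missing counts but does not define it.

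A reader might also infer that an arm doing better would be seen earlier because its children are well. The documents do not support this: V2 is scheduled for D15–D18 for all children, is not triggered by recovery, and allocation is blinded and 1:1. If such children were well, their unobserved days would probably be drug-free anyway.

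The early-leaver example is filtered too. A child whose diary never comes back probably has no post-baseline efficacy data and falls outside the FAS. The problem needs a child who leaves early and still returns the diary, for example at the premature end-of-study visit.

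Finally, the endpoint is secondary, SAP 6.3.1 makes its p-values informational, and the documents give no withdrawal rates. All of this limits the size of the point, but none of it supplies the missing exposure rule.

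**Conclusion.** The point holds as a minor improvement to a descriptive secondary analysis. SAP 10.2.3 uses a fixed window and no exposure term where follow-up varies, and the neighbouring duration endpoints already respect each child's end date. That post-study days act as drug-free days follows from the counting rule rather than from stated text.

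Material bias needs withdrawal that differs by arm. With 10% v 2% withdrawal and front-loaded use, the spurious ratio is about 0.95–0.96 (1.04–1.05 reversed); with equal withdrawal it is 1.00. These figures rest on assumed usage and withdrawal rates. V2 timing alone should matter little.

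It would also be too strong to say that an offset removes the bias. That is true only for a constant daily rate; with front-loaded use, early leavers contribute mainly high-use days and the correction overshoots. The primary analysis and the sample size are not affected.

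**What to change.** In SAP 10.2.3:
- Count days of use from D1 to the earlier of D18 and the reference end date, in line with SAP 10.2.2.
- Add log(observed days) as an offset in the Poisson model. Observed days are the smaller of 18 and the study duration already defined in SAP 11.1, so no new data are needed. For a child lost to follow-up, say which date ends observation.
- State how medications ongoing at end of study are counted. SAP 6.4.5 borrows the adverse-event date rules, and the end-date rules there exclude ongoing events.
- In Mock T16, show observed days by arm and the rate ratio with 95% CI; the Poisson part now shows only Type 3 tests.

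A common cap at D15 is not needed. On its own it leaves the withdrawal bias in place (2.625/2.725 = 0.96 in the same scenario, withdrawal day recorded), and it discards collected days.

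The cost is one derived variable and a few sentences. The downside is the constant-rate assumption: in the 10% v 2% scenario a smaller bias in the opposite direction remains (1.016–1.020). The unadjusted count can be kept as a sensitivity analysis, so that readers see both.
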